6.7. Safety Assessments

Although no study medication is given to subjects during Part A of study AACH, adverse events are routinely collected. A summary of adverse events, reported by MedDRA preferred term, will be displayed by decreasing frequency. A list of adverse events deemed serious will also be created.

7. Part B Analyses

7.1. General Considerations

All analyses will be limited to participants who received study drug and provided clinical, imaging, and/or biomarker data from Part B of AACH.

Baseline definitions are dependent on the quantity being assessed. For safety analyses, baseline will be defined as the last assessment collected prior to the first dose of donanemab, generally Visit 1 from Part B. For treatment-emergent safety analyses, only participants who have both a baseline observation and a postbaseline observation will be included in the analysis for each analyte or parameter, respectively. Where further clarification on baseline definitions is needed, the relevant subsections will specify the definitions.

7.2. Baseline Demographics

Baseline demographics, clinical rating scales, disease characteristics, select concomitant medications, and imaging parameters will be summarized for the safety population.

7.3. Concomitant Medications

Prior medications are defined as those that stop before study drug administration. Concomitant medications are defined as those being taken on or after initiation of study drug. A summary of concomitant medications will be presented as frequencies and percentages.

7.4. Extent of Exposure

Summary statistics will be provided for the total number of complete infusions received by participants during Part B of the study.

7.5. Efficacy Scales

Longitudinal assessment across scheduled visits will be summarized for Part B participants for ADAS-Cog₁₃, ADCS-iADL, iADRS Total Score, CDR Sum of Boxes, and MMSE Total Score.

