**Number of Participants:**

Approximately 200 participants will be enrolled such that approximately 150 participants complete the study.

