### 9.4.3. Secondary Endpoint(s)

To assess the effect of donanemab on clinical progression in participants with symptomatic AD, MMRMs will be fit to the Part B data up to Week 72 for ADAS-Cog13, ADCS-ADL, iADRS, MMSE, and CDR-SB. The models will include terms for visit, age, years of education, and presence/absence of anti-dementia drugs. Visit will be considered a categorical variable.

Observed case analyses will also be conducted for each scale. Additionally, if participant numbers are adequate, AD progression from these models can be compared to anticipated progression had the patient remained untreated. Details of such a comparison are contained in the SAP.

Change from baseline in brain amyloid deposition at Week 36 and Week 72 of Part B will be assessed using an MMRM. The model will include terms for visit, age, years of education, and presence/absence of anti-dementia drugs. Visit will be considered a categorical variable. An observed case analysis will also be conducted.

Change from baseline in brain region volumes at Week 72 for Part B will be assessed using an ANCOVA model. The model will include terms for age, years of education, and presence/absence of anti-dementia drugs. An observed case analysis will also be conducted. The brain regions of interest will be defined in the SAP.

PK analyses will be defined by the PK scientist and will be specified in the PK analysis plan.

Categorical displays of ADAs against donanemab and neutralizing antibodies will be presented.

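### The SAP omits, without explanation, the Part B models that the protocol specifies: the clinical scales are only to be summarised, and the Part B amyloid PET and brain-volume secondary endpoints have no analysis

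*SAP*

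**What the plan says.** Protocol 9.4.3 sets out the analysis of the Part B secondary endpoints.

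- Clinical scales: "MMRMs will be fit to the Part B data up to Week 72", with terms for visit, age, years of education and anti-dementia drug use. Observed-case work is an addition: "Observed case analyses will also be conducted for each scale".
- Amyloid: "Change from baseline in brain amyloid deposition at Week 36 and Week 72 of Part B will be assessed using an MMRM".
- Brain volumes: "Change from baseline in brain region volumes at Week 72 for Part B will be assessed using an ANCOVA model". It adds: "The brain regions of interest will be defined in the SAP".

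The SAP's objectives table (section 4) keeps all of these as secondary endpoints: five clinical scales up to Week 72, Week 36 florbetapir PET and Week 72 volumetric MRI. The analysis chapter for Part B (7.1 to 7.7) has one sentence on efficacy, in 7.5: "Longitudinal assessment across scheduled visits will be summarized for Part B participants", followed by the names of the scales. The rest covers demographics, concomitant medication, exposure, safety, immunogenicity and ARIA.

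Protocol 9.4.1 allows analysis methods to change without an amendment where no principal feature is affected, but requires the change and its justification to be described in the SAP and the study report. The SAP's revision history mentions only Part C analyses and the list of feeder studies.

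**The concern.** The SAP should be the more detailed of the two documents, yet for Part B efficacy it is the less detailed. A by-visit summary with no model and no missing-data rule describes only those who still attend. If participants who decline faster leave earlier, the Week 72 mean understates decline on donanemab. The protocol's MMRM was the safeguard against this, under missing-at-random.

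For amyloid and brain volume the gap is wider: the SAP lists the endpoints but names no method, baseline or brain regions. Part B is open label and its data are available to the sponsor continually (protocol 9.5, SAP 5.3), so any method left open may be chosen after the data have been seen.

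**Working it through.** **Side by side**

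| Part B secondary endpoint | Protocol 9.4.3 | SAP chapter 7 |
|---|---|---|
| Five clinical scales to Week 72 | MMRM, with observed-case in addition | Summarised; no model, covariates or missing-data rule |
| Amyloid PET | MMRM at Weeks 36 and 72 | No analysis |
| Volumetric MRI, Week 72 | ANCOVA; regions left to the SAP | No analysis; regions not defined |

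Two further checks show that this is not simply a brief style. First, the same SAP gives formulas or full models for Part A (6.5, 6.6) and for Part C (8.6 to 8.8). Second, other details that the protocol hands to the SAP are also absent for Part B: the prorating rules for missing ADAS-Cog13 and ADCS-ADL items (9.4.1) and the comparison with expected untreated progression (9.4.3). SAP 7.1 defines a Part B baseline for safety only and leaves others to the relevant subsections; 7.5 gives none.

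**Can the protocol's models be copied as they stand?** Not entirely.
- The Part B schedule shows one planned florbetapir scan, at Week 36, and Appendix 5 counts one scan in total. There is no Part B baseline scan and no Week 72 scan, so a repeated-measures model over Weeks 36 and 72 cannot be fitted.
- An MRI before Visit 1 is required only if the last one from the originating study is more than 12 months old (protocol 6.1), so the baseline MRI needs defining too.
- Protocol 9.4.3 names ADCS-ADL for the MMRM, whereas the endpoint tables in both documents and SAP 7.5 name ADCS-iADL.

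**Size: inputs.** The documents give no Part B sample size, dropout rate or expected change. What they do give is 200 enrolled, about 180 completing Pair 1 and about 150 completing the study (protocol 9.2). The only stated power figure, 81%, concerns Part A. Simulation reproduces it closely at n = 180 (82.5%, mean ICC 0.793, mean interval 0.732 to 0.842), but it has no bearing on Part B.

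**Loss.** Of the 200 − 150 = 50 expected losses, 200 − 180 = 20 fall before Pair 1 is complete, and Pair 1 should precede Part B (protocol 4.1.3). That leaves at most 30 of 180, or 16.7%, pooled over everything after Pair 1. Part B's own rate may lie on either side.

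**Bias formula.** With a share d lost and an extra decline Δ in those lost compared with those who stay, the observed mean is too favourable by d × Δ. Taking Δ = 0 to 4 ADAS-Cog13 points (assumption):
- d = 16.7%: 0.167 × 0 to 4 = 0 to 0.67 point
- d = 10% (assumption): 0 to 0.4 point
- d = 25% (assumption): 0 to 1.0 point

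**How much an MMRM would recover.** Single-arm simulation of 400 runs with n = 80 and a true Week 72 change of 6 points. The SD of change is 5.46, from √(8² + 9² − 2 × 0.8 × 8 × 9) = √29.8, borrowed from the Part A assumptions. Lag-1 correlation is 0.8, and dropout depends on the last observed change. All of these are assumptions. Bias of the observed-case mean, in points:

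| Dropout by Week 72 | Log-odds 0 per SD | 0.5 per SD | 1.0 per SD |
|---|---|---|---|
| 10% | 0.01 | −0.11 | −0.24 |
| 25% | 0.09 | −0.42 | −0.64 |
| 40% | −0.01 | −0.71 | −1.23 |

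The maximum-likelihood estimate, equivalent to an unstructured MMRM for monotone dropout, stayed within 0.1 point throughout. The 0.09 in the zero column appears for both estimators and is simulation noise. Dropout here is missing-at-random by construction, the setting that favours the MMRM. Where dropout depends on unobserved decline, an MMRM removes only part of the bias.

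**The case against.** The strongest reply is that the stakes are limited. Part B has no statistical hypotheses, no control group and a safety primary objective, so no test, error rate or power changes. That stands, and it keeps this a recommended correction, not a threat to the study's primary conclusions.

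The wording also needs care. A reader might infer that the SAP has replaced the MMRM with an observed-case analysis. It does not say so: SAP 8.6 to 8.8 open with the same language of summarising and go on to specify an ANCOVA. In 7.5 no model follows, so the defect is an unexplained omission; reading it as observed cases is a fair inference, not a stated rule. Nor does the SAP revoke protocol 9.4.3, so it is not established that the models will not be run.

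A reader might also infer that the SAP has no amyloid PET analysis at all. SAP 8.7 models florbetapir PET, but for Part C participants. Part B participants enter chapter 8 only as untreated comparators with pre-treatment data, so the Part B Week 36 endpoint remains uncovered.

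Finally, one might take 25% dropout from "Approximately 200 participants will be enrolled such that approximately 150 participants complete the study" and conclude that the bias is at least half a point. That figure covers the whole study, including 20 losses expected before Pair 1 is complete, and the bias is nil if dropout is unrelated to outcome.

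**Conclusion.** The mismatch is real and can be confirmed by reading: the SAP omits the Part B models in protocol 9.4.3, leaves two listed secondary endpoints without an analysis and gives no justification. If the SAP is followed as written, the ADAS-Cog13 mean change at Week 72 is too favourable by 0 to about 0.7 point. That range rests on the pooled 17% loss after Pair 1 standing in for Part B dropout, and on an assumed 0 to 4 points of extra decline in those lost. It is not all attributable to leaving out the MMRM, which removes only the part predictable from observed data. For amyloid PET and brain volume the consequence is not a numerical bias but an undefined analysis. Restoring protocol 9.4.3 word for word would not be enough, because its amyloid model does not match the scan schedule and its functional scale does not match the listed endpoint.

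**What to change.** Before the Part B data are analysed:

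1. In SAP 7.5, make an MMRM of change from Part B baseline the main analysis for MMSE, ADAS-Cog13, iADRS, ADCS-iADL and CDR-SB. Use the protocol's terms (categorical visit, age, years of education, anti-dementia drug use) and add baseline score, which protocol 9.4.3 does not list. Define the efficacy baseline and keep observed-case summaries as supportive. Reconcile ADCS-ADL in protocol 9.4.3 with the listed ADCS-iADL.
2. Add an ANCOVA of Week 36 amyloid change that names the scan serving as baseline, since none is scheduled in Part B. Correct the Week 72 amyloid term in protocol 9.4.3.
3. Add the Week 72 brain-volume ANCOVA, with the brain regions and the baseline MRI defined.
4. If any of these models is deliberately dropped, record this and justify it in the SAP, as protocol 9.4.1 requires.

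The cost is SAP text, a small protocol correction and standard programming. No new data are needed, and no sample size or power figure changes.

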7.6. Safety Analyses

The following subsections describe the summaries of safety information that will be presented for the Part B database lock. All analyses contained in the subsections below will be based on the safety population of the study.

7.6.1. Adverse Events

A treatment-emergent adverse event (TEAE) is defined as an event that first occurred or worsened after the first donanemab infusion. The Medical Dictionary for Regulatory Activities (MedDRA) Lowest Level Term (LLT) will be used in the treatment-emergent computation. The version of MedDRA that will be used is the most recent version available at the time of database lock. The maximum severity for each LLT during the baseline period will be used as baseline. The treatment period will be included as post-baseline for the analysis. While unusual, it is possible to have a missing severity for events. For events with a missing severity during the

baseline period, it will be treated as “mild” in severity for determining treatment emergence. Events with a missing severity during the postbaseline period will be treated as “severe” and treatment emergence will be determined by comparing with baseline severity.

The planned summaries for adverse events (AEs) are provided in the table below.

Tables and Figures Related to Adverse Events

Analysis	Details	Analysis Set/Population
Overview of AEs	Number and percentage of participants who experienced 
 • TEAE • SAE • death, and • discontinuation from study treatment due to an AE. 	Safety Population
TEAEs by PT within SOC	Number and percentage of participants with TEAEs using MedDRA PT nested within SOC	Safety Population
SAEs by PT	The number and percentage of participants who experienced an SAE (including deaths and SAEs temporally associated or preceding deaths) using MedDRA PT	Safety Population
AEs Reported as Reason for Treatment Discontinuation by PT	Number and percentage of participants reporting an AE as the reason for discontinuing study treatment using MedDRA PT	Safety Population

Abbreviations: AE = adverse event; SAE = serious adverse event; MedDRA = Medical Dictionary for Drug Regulatory Activities; PT = preferred term; SOC = System Organ Class; TEAE = treatment-emergent adverse event.

7.6.2. Clinical Laboratory Evaluations

Laboratory measurements will be analyzed using continuous data (change from baseline) and categorical or ordinal data (proportion of treatment-emergent abnormalities). If there are multiple records of laboratory measurements at baseline or postbaseline visit, the last record will be used. Summaries and analyses of continuous data (change from baseline) will be performed using both conventional and International System of Units (SI units).

Mean changes from baseline to scheduled post-baseline visits will be summarized for chemistry and hematology lab parameters.

The number and percentages for hematology and chemistry laboratory observations that fall outside of reference limits will be summarized. The reference limits from the performing laboratory will be used to define low and high. For a given lab parameter, a value is counted as treatment-emergent low if the minimum post-baseline value is categorized as low and the baseline value was classified as either normal or high. Similarly, a value is counted as treatment-

emergent high if the maximum post-baseline value is categorized as high and the baseline value was classified as either normal or low. All post-baseline lab assessments will be included in the analyses, whether scheduled or unscheduled.

In addition, for hepatic lab values, clinically significant changes of interest at any time are: ALT $\geq 3 \times$ upper limit of normal (ULN), AST $\geq 3 \times$ ULN, ALT $\geq 5 \times$ ULN, ALT $\geq 10 \times$ ULN, and total bilirubin $\geq 2 \times$ ULN. Additionally, Hy's Law analysis will be conducted by comparing treatment groups with regard to the proportion of patients with (ALT $\geq 3 \times$ ULN OR AST $\geq 3 \times$ ULN) AND total bilirubin $\geq 2 \times$ ULN at any time.

7.6.3. **Electrocardiogram Parameters**

ECG measurements will be analyzed using continuous data (change from baseline) and categorical data (proportion of treatment-emergent abnormalities).

Analysis will be done for the following ECG measurements: heart rate, PR, QT, QTc, and RR intervals and QRS duration. All analyses of QTc will be carried out using the Fridericia correction (QTcF) method. These summaries will include data from each scheduled visit at which ECG measures are performed. Mean change from baseline to each post-baseline visit at which ECG measurements are taken will be summarized.

Incidence of treatment-emergent abnormal ECGs will be assessed by comparisons at (1) anytime and (2) each post-baseline visit. Abnormal ECG criteria and criteria for abnormal QTcF prolongation are presented below:

ECG Parameter	Low Criteria	High Criteria
Heart Rate	<50 bpm	>100 bpm
PR Interval	<120 msec	≥ 220 msec
QRS Duration	<60 msec	≥ 120 msec
QTcF Interval		
Males	<330 msec	≥ 450 msec
Females	<340 msec	≥ 470 msec
Males and females		> 500 msec

Abbreviations: bpm = beats per minute; ECG = electrocardiogram; QTcF = Fridericia-corrected QT interval.

Treatment-emergent high ECG parameters (heart rate, PR interval, QRS duration, QT and QTcF intervals) are the values which are low or normal at all baseline visits and fall into the high abnormal categories post-baseline. Similarly, treatment-emergent low ECG parameters (heart rate, PR interval, QRS duration) are the values which are high or normal at all baseline visits and fall into the low abnormal categories above.

7.6.4. Vital Signs and Weight

Vitals signs and weight will be analyzed using continuous data (change from baseline) and categorical data (proportion of treatment-emergent abnormalities).

Analysis will be done for all collected vital signs and weight parameters. These summaries will include data from each scheduled visit at which vital signs are performed. Mean change from baseline to each post-baseline visit at which vital signs are taken will be summarized.

The number and percentage of participants with observations exceeding defined limits on vital signs and weight will be summarized. The measures of interest and their corresponding limits are as follows:

Vital Sign Parameter (Unit)	Postbaseline Low Criteria	Postbaseline High Criteria
Sitting systolic blood pressure (mmHg)	Absolute value ≤ 90 and ≥ 20 decrease from baseline	Absolute value ≥ 160 and ≥ 20 increase from baseline
Sitting diastolic blood pressure (mmHg)	Absolute value ≤ 50 and ≥ 10 decrease from baseline	Absolute value ≥ 100 and ≥ 10 increase from baseline
Sitting pulse (bpm)	Absolute value < 50 and ≥ 15 decrease from baseline	Absolute value > 100 and ≥ 15 increase from baseline
Weight	$\geq 7\%$ decrease	$\geq 7\%$ increase
Vital Sign Parameter (Unit)	Postbaseline Criteria for Abnormality	
Orthostatic systolic blood pressure (mmHg)	≥ 20 mmHg decrease in systolic blood pressure (supine to standing) (i.e., supine minus standing ≥ 20)	
Orthostatic diastolic blood pressure (mmHg)	≥ 10 mmHg decrease in diastolic blood pressure (supine to standing) (i.e., supine minus standing ≥ 10 mm Hg)	
Orthostatic pulse (bpm)	≥ 30 increase in bpm (standing to supine) (i.e., standing minus supine ≥ 30)	
Temperature	Absolute value $\geq 38.3^{\circ}\text{C}$ and $\geq 1.1^{\circ}\text{C}$ increase from baseline (Absolute value $\geq 101^{\circ}\text{F}$ and $\geq 2^{\circ}\text{F}$ increase from baseline)	

Abbreviation: bpm = beats per minute.

7.6.5. Columbia Suicide Severity Rating Scale (C-SSRS)

Suicidal ideation, suicidal behavior, and self-injurious behavior without suicidal intent, based on the Columbia-Suicide Severity Rating Scale (C-SSRS), will be listed by patient and visit. Only patients that show suicidal ideation/behavior or self-injurious behavior without suicidal intent will be displayed (ie, if a patient answers are all ‘no’ for the C-SSRS, then that patient will not be displayed). However, if a patient reported any suicidal ideation/ behavior or self-injurious behavior without suicidal intent at any time point, then all their ideation and behavior will be displayed, even if not positive.

7.6.6. Immunogenicity

Subject samples will be analyzed using a 4-tiered approach. All samples will be assessed in Tier 1 (screening) for the possible presence of ADA. Samples found to produce a signal above or equal to the screening cut point will be assessed in Tier 2 to confirm specificity to LY3002813 (confirmation). Any samples confirmed as specific for anti-LY3002813 antibodies will be reported as “detected.” All samples below the screening cut point (Tier 1) or not confirmed (Tier

2) will be reported as “not detected.” Any “detected” sample in Tier 2 will be assessed in Tier 3 (titer assessment) and Tier 4 (neutralizing antibodies). Anti-drug antibodies titer values will be reported from Tier 3 titer assessment. Any samples above the Tier 4 assay cut point will be reported as “detected for neutralizing antibodies”; samples below the assay cut point in Tier 4 will be reported as “not detected for neutralizing antibodies.”

The frequency and percentage of subjects with preexisting (baseline) ADA, ADA at any time after baseline, and treatment-emergent ADA (TE-ADA) to LY3002813 will be summarized. If no ADAs are detected at baseline, TE-ADA are defined as those with a titer 2 fold (1 dilution) greater than the minimum required dilution (MRD) of the assay (the MRD for anti-LY3002813 antibody assay is 10). For samples with ADA detected at baseline TE-ADA are defined as those with a 4-fold (2 dilutions) increase in titer compared to baseline. For subjects with TE-ADA, the distribution of maximum titers during double-blind treatment period will be described via a baseline to post-baseline shift table. The frequency of neutralizing antibodies may also be tabulated.

7.6.7. Amyloid-Related Imaging Abnormalities (ARIA)

Scheduled and unscheduled magnetic resonance imaging (MRI) will be used to present ARIA events. An overview of ARIA incidence will be presented using frequency and percentage of subjects with any ARIA (ARIA-E or ARIA-H), ARIA-E, and ARIA-H as defined by safety MRIs or TEAE cluster. ARIA-E TEAE Cluster PT are defined as amyloid-related imaging abnormality oedema/effusion, brain oedema, vasogenic cerebral oedema. ARIA-H TEAE Cluster PT are defined as amyloid-related imaging abnormality-microhaemorrhage and haemosiderin deposits, brain stem microhaemorrhage, cerebellar microhaemorrhage, cerebral hemosiderin deposit, cerebral microhaemorrhage, superficial siderosis of the central nervous system, cerebral haemorrhage.

The frequency and percentages of ARIA-E will be further broken out by asymptomatic vs. symptomatic. The frequency and percentage of subjects with ARIA-H microhemorrhage, ARIA-H superficial siderosis, and ARIA-H macrohemorrhage on safety MRI will be reported.

A table displaying the shift ARIA-H event from baseline by visit will be created based on safety MRI. ARIA-E shift table based on safety MRI will be displayed using a 5-point rating scale (mild, mild+, moderate, moderate+, severe).

7.7. Subgroup Analyses

No subgroup analyses are planned for the safety population.

8. Part C Analyses

